10.4 Decisional Regret Scale

The Decisional Regret Scale⁷³ is a short, 5-item scale measuring "distress or remorse after a (health care) decision." The instrument has been validated in other decision aid studies.⁷⁴ Questions are answered on a 5-point agreement scale.

The questionnaire will be administered once; 12 months after the patient's initial consultation and will take approximately 1-3 minutes to complete.

11.0 END OF INTERVENTION

11.1 Duration of Treatment

The study intervention will take place in one day and follow-up assessments will occur at 12 months following the intervention.

11.2 Managing ineligible patients and registered patients who never receive protocol intervention

Definition of ineligible patients

A study participant who is registered to the trial but does not meet all of the eligibility criteria is deemed to be ineligible.

Follow-up for ineligible patients who continue with protocol intervention

Patients who are deemed ineligible after registering may continue the protocol intervention, provided the treating physician, study chair, and executive officer agree there are no safety concerns if the patient continues protocol intervention. All tests and data submission are to continue as if the patient were eligible. Notification of the local IRB may be necessary per local IRB policies.

Follow-up for ineligible patients who discontinue protocol intervention

For patients who are deemed ineligible after registering to the trial, who start the study intervention, but then discontinue the intervention, the same data submission requirements are to be followed as for those patients who are eligible and who discontinue study participation.

Follow-up for patients who are registered, but who never start study intervention

For all study participants who are registered to the trial but who never receive study intervention (regardless of eligibility), baseline and off-treatment notice data submission required. See the Data Submission Schedule accompanying the All Forms Packet.

11.3 Extraordinary Medical Circumstances

If, at any time the constraints of this protocol are detrimental to the patient's health and/or the patient no longer wishes to continue protocol participation, protocol participation shall be discontinued. In this event:

- Document the reason(s) for discontinuation of protocol participation on data forms.
- Follow the patient for protocol endpoints as required by the Study Calendar.

12.0 STATISTICAL CONSIDERATIONS

12.1 Study Design

This is a non-treatment study evaluating Decision Aids (DAs) for patients with newly diagnosed prostate cancer. For this trial, participating institutions are randomized, according to the racial distribution of the patient population, to treat patients to one of 4 treatment arms (see Schema). Patients will complete on-line DAs if not randomized to the Usual Care arm. All patients will complete a baseline knowledge questionnaire after the initial clinic visit and at 12-months following the surgical consultation.

12.2 Statistical Design and Analysis for the Primary Endpoint

Primary Endpoint: The primary outcome, knowledge, will be assessed by a standardized questionnaire (i.e., Prostate Cancer Treatment Questionnaire) administered once, immediately after the clinical consultation while the patient is still at the study site. The number correct from this 12-item measure will be reduced to a percentage of total number correct.

A different method for measuring our primary outcome, knowledge, proposing instead a pre-post approach was considered. However, several factors lead us to favor a one-time post-intervention measurement: 1) Our study's randomized design should control for differences in baseline effects; 2) a pre-post design could be confounded by learning effects associated with the baseline measurement since the baseline and post-intervention measurements would only be 1-2 hours apart. Such learning affects could lead to artificial improvements in our control group which could limit our ability to see "true" differences attributable to the intervention(s); 3) finally, a one-time measurement of knowledge will minimize burden to respondents, particularly during the consenting and baseline measurement period where we seek to impede clinical workflows as little as possible.

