Decision aids can improve patient knowledge and patient-provider communication by presenting risk information and helping elicit patient preferences. They improve knowledge and reduce treatment regret in prostate cancer treatment.⁴⁴⁻⁴⁷ Decision aids can mitigate low literacy effects in disparities by decreasing the demands required for patients to make an informed treatment decision. They better align the task of decision making with the skills and abilities of patients.^{48,49} In other clinical conditions, decision aids have been successfully used to reduce disparities in self-reported symptoms and patient knowledge.⁵⁰ Moreover, a recent systematic review entitled “Interventions to Improve Decision Making and Reduce Racial and Ethnic Disparities in the Management of Prostate Cancer” among screening eligible men suggests that educational programs can improve knowledge and interventions that proactively include discussion of quality of life can improve quality of life outcomes.⁵¹ Educational interventions like these seem to have greater effect in men with less than a college education, thereby neutralizing disparities associated with education and literacy.⁵² Thus, decision aids are a plausible health system intervention that could be delivered in the specialty care context to reduce disparities in knowledge and functional outcomes potentially mediated by poor communication, that will work even in patients with low health literacy. Existing prostate cancer treatment decision aids have a variety of features summarized below.

Author/ Date	Report Minority	Delivery Mode	Delivery Context	Pro- prietary	Tailor Risk	Comment
Davison & Degner 1997	No	Written Information package + consultation with nurse + (optional) audiotape of visit vs. Written information only	Inside specialty visit	N/A	No	Lower anxiety in the intervention group ($p < .005$)
Auvinen 2004		Extensive consultation with urologist + patient defined own role in decision making vs. standard treatment protocol	Inside specialty visit			20% fewer men chose surgery in the intervention group vs. the control group (63% vs. 85%)
Davison 2007		Personalized treatment information + generic video + written information vs. generic video + written information	Patient education center			No group differences

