12.2.1 Analysis Plan

Although the randomization unit will be participating site, our inferential unit for statistical analysis will be the individual patient. Due to the potential for correlation among patients within the same site, a mixed effects regression model (also known as random effects model or multi-level model) will be utilized to examine the effects of the during-consultation Prostate Choice and the pre-consultation Knowing Your Options decision aids. Specifically, this model will contain a fixed intercept, a fixed effect for having received Prostate Choice, a fixed effect for having received Knowing Your Options, and a random, site-specific intercept to allow patients within the same site to be correlated. Baseline patient-level characteristics including race, ethnicity, severity of disease and site-level characteristics may be incorporated in this model if deemed appropriate. A similar approach will be utilized in the statistical analysis of secondary endpoints. Furthermore, descriptive statistics will be reported after incorporating cluster information, in particular, the empirical cluster size, and the observed intra-cluster correlation.

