12.2.2 Sample Size and Power Considerations

Sample size and power calculation: We first consider power and sample size under the assumption that patients within the same site are uncorrelated. As this is unlikely to be the case in a group randomized trial, we will discuss the adjustment of the sample size estimate to account for this correlation between patients in the next subsection. A recent Cochrane review suggests that most patients can accurately answer 50% (standard deviation of 12%) of the questions asked of them.⁷⁰ On average, DAs increase that knowledge by 20% to 60% of questions asked being answered correctly, but 95% of trials show absolute knowledge increases of 10% or greater. We will consider an absolute 8% increase in knowledge as a clinically meaningful effect size for either during-consultation Prostate Choice or pre-consultation DA in this clinical trial. Note that the four arms of this study make up a 2 X 2 factorial design. Thus, it is natural to consider evaluating the decision aids using a two-way analysis of variance (ANOVA). In this case, the two factors in the ANOVA will be having received during-consultation Prostate Choice (yes or no) and having received pre-consultation DA (yes or no). We will consider simultaneously testing (at a significance level of 0.025 for each test) the main effects of the two decision aids as our primary analysis. That is, we will simultaneously test the null hypothesis that the average knowledge (i.e. the proportion of correct responses to questions) among those who received the pre-consultation DA is equal to that among those who did not (vs. an alternative that these two averages are not equal), and the null hypothesis that the average knowledge among those who received the during-consultation Prostate Choice is equal to that among those who did not (vs. an alternative that these two averages are not equal). A total sample of 100 patients (25 patients per arm) would give us approximately 85% power to detect a difference between those receiving pre-consultation DA and those not receiving pre-consultation DA, under the alternative that the average knowledge among those receiving pre-consultation DA is 58%, and that the average knowledge among those not receiving pre-consultation DA is 50%, using a two-sample t-test (with two-sided alternative) with a 2.5% significance level (this is equivalent to the F test for the main effects in the ANOVA). Under a similar alternative, the same can be said for the during-consultation Prostate Choice decision aid. Thus, if patients within each site were not correlated with each other, our target sample size would be 100 patients. There will be some, but insufficient power to detect an interaction between the two decision aids, but such effects are rare and not anticipated in this study. Therefore, we will not test for such an interaction in the primary analysis.

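### Education is neither specified for collection nor named as a covariate in the primary knowledge model: a cheap gain in precision, not a source of bias

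*Combined protocol and SAP*

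**What the plan says.** Section 12.2 sets one post-consultation measurement of the 12-item knowledge score. It gives three reasons for rejecting a pre-test: the "randomized design should control for differences in baseline effects"; a learning effect when two tests fall within an hour or two; and the burden on respondents and clinics.

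Section 12.2.1 specifies a mixed model with a fixed effect for each decision aid and a random site intercept. On covariates it says: "Baseline patient-level characteristics including race, ethnicity, severity of disease and site-level characteristics may be incorporated in this model if deemed appropriate". Nothing is committed, and education is not on the list.

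Section 1.1 says of educational programs: "Educational interventions like these seem to have greater effect in men with less than a college education". It also argues that decision aids can offset the effects of low literacy.

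The baseline questionnaire (section 5.0 and Appendix I) holds the knowledge items and the Decisional Conflict Scale. The 12-month booklet (Appendix II) holds EPIC-26 and the regret scale. None of these, and none of the measures in section 10, includes education. Section 6.1 refers to a schedule of forms kept on the study webpage, which is not in the document.

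Section 4.3 stratifies site randomization by center type. Section 4.5 says these groupings are not formal stratification factors but still spreads the sites over the arms.

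**The concern.** Randomization balances baseline knowledge on average. With 20 randomized units it balances only loosely in any one trial, and without a pre-test the most predictive covariate is unavailable. A patient characteristic that predicts the score and that the visit cannot change is the natural partial substitute. The protocol's own background points to education, yet the analysis plan does not use it.

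Two things are at stake. The first is precision: variation in knowledge that education could explain stays in the standard error of each aid's effect. The second is prespecification: covariates that enter only if judged appropriate can be chosen after the data are seen, whereas a covariate named in advance cannot. If the forms turn out not to record education, the option is lost once enrollment ends.

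**Working it through.** **Inputs from section 12.2.2.** Each main effect is tested "at a significance level of 0.025 for each test", two-sided. The target is 8 points and the SD 12 points. The plan expects intra-site correlation 0.1, 20 sites, and 172 men enrolled, inflated from 140. With equal allocation that is 5 sites per arm, so 10 against 10 sites for each aid.

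**The plan's own figure.** For 100 uncorrelated men, SE = 12 × √(4/100) = 2.40. The noncentral t with 98 df gives power 85.3%, which agrees with the stated approximate 85%.

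**Variance split.** Between sites: 0.1 × 144 = 14.4 (SD 3.8 points). Within sites: 144 − 14.4 = 129.6.

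**Chance imbalance between sites.** The site part of a 10-against-10 difference has SD √(14.4 × 2/10) = 1.70 points, a 95% range of ±3.3. This is one component of the SE below, not an addition to it.

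**SE of a main effect.** Let education explain a share *a* of site variance and *b* of patient variance:

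SE² = 4 × [14.4(1 − a)/20 + 129.6(1 − b)/N]

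With N = 172 and a = b = 0: 2.880 + 3.014 = 5.894, so SE = 2.43.

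**Power for 8 points, two-sided 2.5%, N = 172.** The 17 df are 20 sites less three fixed effects (intercept and two aids). The last column uses patient-level df. All values of *a* and *b* are assumptions.

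| a (site) | b (patient) | SE | Power, 17 df | Power, patient df |
|---|---|---|---|---|
| 0 | 0 | 2.43 | 79.0% | 84.8% |
| 0 | 0.05 | 2.40 | 80.1% | 85.8% |
| 0.05 | 0.05 | 2.37 | 81.2% | 86.7% |
| 0.10 | 0.05 | 2.34 | 82.3% | 87.7% |
| 0.10 | 0.10 | 2.30 | 83.4% | 88.6% |
| 0.30 | 0.05 | 2.21 | 86.6% | 91.2% |
| 0.50 | 0.10 | 2.04 | 91.7% | 95.1% |

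**If only 140 men are analysed.** On 17 df, power goes from 74.0% with no covariate to 76.3% at a = b = 0.05 and 78.8% at a = b = 0.10. On patient-level df it goes from 80.2% to 82.3% and 84.5%.

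**How far education alone could move the comparison.** Assume that education shifts the score by 5 to 10 points, that 30–50% of men are in the higher group, and that education has an intra-site correlation of 0.05–0.20. The chance shift at N = 140 then has a 95% range of about ±0.9 to ±2.5 points, against a target of 8.

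**The case against.** The strongest reply is that the trial already handles this. Chance differences between sites are sampling variation. The random site intercept carries them into the standard error, so the test stays valid and there is no bias in expectation. That is correct, and it limits the point to precision. A reader might infer from the ±3.3 points that the estimates are biased; the document does not support that.

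A reader might also infer that the trial collects no education data. That cannot be shown. Race and ethnicity are absent from the booklets too, yet they are candidate covariates and drive the accrual limits, so some demographics must be recorded on forms outside the document. What can be said is that no education item is specified.

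Nor does the plan rely on randomization alone. Site assignment takes account of center type, and the optional covariates include site-level characteristics, the level at which imbalance arises. Race and center type may overlap with education, which would shrink the gain. Learning effects and burden remain good reasons for having no pre-test, but neither applies to a single education question.

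The background sentence on education describes a larger effect in less-educated men, which is effect modification. It does not show that education predicts the score, and a main-effect covariate would not address effect modification. This objection stands, and it is why the gain has to be given as an assumed range.

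Finally, the 79% start depends on using 17 df. Section 12.2.1 names no df method, and the plan's power calculation uses a patient-level t-test, on which 172 men give 85% with no covariate.

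**Conclusion.** The point holds as an inexpensive improvement in precision. With one post-visit measurement and about 10 against 10 sites per aid, the primary model leaves its covariates optional and omits a characteristic that the background treats as relevant.

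Under modest assumptions (0–10% of site variance and 5–10% of patient variance explained), the gain at 172 men is about 1 to 4 percentage points of power: 79% to 80–83% on 17 df, or 85% to 86–89% on patient-level df. Reaching 87–92% on 17 df needs education to explain 30–50% of site variance, for which the document offers no support. The figures rest on SD 12, intra-site correlation 0.1, equal allocation of sites, all 172 men analysed, and no other covariate in the model. The primary analysis is valid without the change.

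**What to change.** 1. Confirm whether the registration or case report forms record education.
2. If they do not, add one self-reported item, highest level of education, to the registration form or the Appendix I booklet. The consultation cannot alter the answer, so asking afterwards is safe.
3. In either case, name education in section 12.2.1 as a prespecified fixed covariate in the primary mixed model, with missing answers as a separate category.
4. Keep the single post-visit knowledge measurement.

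The cost is one tick-box and one model term, with no extra visits or staff. The downside is small: the gain shrinks if education largely duplicates race, ethnicity or center type.

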12.2.1 Analysis Plan

Although the randomization unit will be participating site, our inferential unit for statistical analysis will be the individual patient. Due to the potential for correlation among patients within the same site, a mixed effects regression model (also known as random effects model or multi-level model) will be utilized to examine the effects of the during-consultation Prostate Choice and the pre-consultation Knowing Your Options decision aids. Specifically, this model will contain a fixed intercept, a fixed effect for having received Prostate Choice, a fixed effect for having received Knowing Your Options, and a random, site-specific intercept to allow patients within the same site to be correlated. Baseline patient-level characteristics including race, ethnicity, severity of disease and site-level characteristics may be incorporated in this model if deemed appropriate. A similar approach will be utilized in the statistical analysis of secondary endpoints. Furthermore, descriptive statistics will be reported after incorporating cluster information, in particular, the empirical cluster size, and the observed intra-cluster correlation.

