Thus, the denominator of our test statistic should actually be $[(4\sigma^2/n)(1 + (m-1)\rho)]^{(1/2)}$. Therefore, if we replace the original sample size ($n=100$) with $n(1 + (m-1)\rho) = 100*1.4 = 140$ in the denominator of our original test statistic, we will have a test statistic which accounts for the correlation of 0.1 between subjects within each of the 20 sites. Hence, we will target an effective sample size of 140 patients (approximately 35 patients per arm, 7 patients per site). The total sample size may be further inflated by 20% to account for ineligible, cancel and loss to follow-up for longer term secondary outcomes and allow increased power to detect racial/ethnic differences. Therefore, a total number of 172 patients will be enrolled into this clinical trial. These 172 patients, recruited from 20 participating sites (about 9 patients per site) will receive the intervention (or control) to which their location is randomized.

Though we have chosen to power this study based on an absolute meaningful difference of 8%, we determined the necessary sample size for a range of meaningful differences. In each case, the target power was approximately 85% (thought it varied slightly, as we only considered sizes which were divisible by 20, given the number of expected sites) with joint main effect two-sided t-tests with two-sided alternatives at the 2.5% significance level. These sample sizes are as follows (not adjusted for ineligibility, cancel and loss to follow-up):

Meaningful Difference	Total sample size without correlation within sites	Total sample size adjusted for correlation within sites
4%	360	504
6%	180	252
8%	100	140
10%	60	84
12%	40	56

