12.4.2 Secondary analyses

Decisional quality, average clinical time required, and patient QOL scores will be compared across DA types using linear mixed models similar to that used to assess the primary endpoint. In particular, this model will include fixed effects for Prostate Choice and Knowing Your Options and a random, site-specific intercept to allow for subjects within the same site to be correlated. Utilization will be compared across DA types using a generalized linear mixed model, again with fixed effects for having received Prostate Choice and having received Knowing Your Options and a random, site-specific intercept.

As mentioned above, the primary analysis will be re-implemented within only minority men as a secondary analysis. We anticipate enrolling approximately 80% minority men. It is worth noting that, if this were the primary analysis, this sample would give us approximately 78% power to detect an absolute difference of 8% in knowledge for either of the decision aid main effects using a two-sample t-test (with two-sided alternative) with a 2.5% significance level (i.e. the same analysis/assumptions used to power the primary analysis).

As an additional secondary objective, we will explore whether the overall effects of interventions on patient knowledge, quality of life, and treatment utilization differ by racial/ethnic subgroups. Our sample size is driven by the primary outcome of knowledge. Oversampling of minority populations of interest will achieve a robust representation of these minority populations in our final sample, but we have not designed the trial to have sufficient power to ascertain subtle subgroup differences in knowledge and quality of life by race/ethnicity subgroups. These secondary analyses will be exploratory, because fully testing the racial/ethnic differences would require prohibitively large sample sizes, and the literature does not suggest a strong race-based rationale for large differences. If subtle but potentially important trends in subgroup differences are identified in these exploratory analyses, those findings could be used to justify a larger study examining a primary hypothesis related to racial/ethnic difference or could influence the design of subsequent culturally tailored interventions. At present, the science of decision aids and the state of the evidence surrounding racial/ethnic differences in the effect of decision aids would not support testing such a hypothesis as a primary endpoint.

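### The 85% power uses patient-level degrees of freedom for a comparison among about 20 sites, and the primary model names no small-sample method; with site-level degrees of freedom, power is about 79-80%.

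*Combined protocol and SAP*

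**What the plan says.** Section 4.3 randomizes institutions and gives every man at an institution that institution's arm. Section 12.2.1 then says: "Although the randomization unit will be participating site, our inferential unit for statistical analysis will be the individual patient". Its primary model is a mixed model with an intercept, one fixed effect per aid and a random intercept for site. It does not say whether the fit is by maximum likelihood or REML, or what reference distribution the tests use.

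Section 12.2.2 tests the two main effects "at a significance level of 0.025 for each test". On the target difference: "We will consider an absolute 8% increase in knowledge as a clinically meaningful effect size". For the control level it reports that "most patients can accurately answer 50% (standard deviation of 12%) of the questions asked of them". On power: "A total sample of 100 patients (25 patients per arm) would give us approximately 85% power", obtained "using a two-sample t-test (with two-sided alternative) with a 2.5% significance level". With 20 expected sites and an intra-site correlation of 0.1, it multiplies 100 by 1.4 to reach 140, and says that in this way "we will have a test statistic which accounts for the correlation of 0.1 between subjects within each of the 20 sites". Enrollment is then set at 172.

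For the re-analysis in minority men, Section 12.4.2 says that "this sample would give us approximately 78% power to detect an absolute difference of 8% in knowledge", using the same test and assumptions.

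**The concern.** Neither aid varies within a site. However many men each site enrolls, the evidence about an aid comes from comparing about ten sites with about ten others. The design effect in 12.2.2 corrects the size of the standard error. It does not correct for that standard error being estimated from only about 20 site-level observations, which calls for a t distribution with far fewer degrees of freedom than there are patients.

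Two things are at stake. The stated power is not delivered by a test that holds its level. And because 12.2.1 leaves the method open, a software default could settle the critical value for both primary tests, and so the width of their confidence intervals. The plan splits alpha to 2.5% per test to keep the overall error at 5%; an uncorrected test would undo part of that protection. The linear models for secondary endpoints in 12.4.2 reuse the same approach.

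**Working it through.** **Inputs.** From 12.2.2: difference 8 points, SD 12, two-sided 2.5% per test, intra-site correlation 0.1, 20 sites, design effect 1.4 (computed at 5 men per site), target 140 (7 per site), enrollment 172 (172/20 = 8.6 per site). From 12.2.1: an intercept and two fixed effects, so site-level degrees of freedom (df) are 20 - 3 = 17. Equal site sizes are assumed.

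**Reproducing the plan's figure.** With 100 independent men, the noncentrality is 8/(12 × √(4/100)) = 8/2.4 = 3.333. On 98 df the critical value is 2.276 and power is 85.3%, matching the stated 85%. Also 100 × 1.4 = 140.

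**Changing only the degrees of freedom.** Noncentrality = 8/(12 × √(4 × DE/N)), with DE = 1 + (m - 1) × 0.1 unless the plan's 1.4 is kept. On 17 df the critical value is 2.458.

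| Case | DE | Noncentrality | Power, patient-level df | Power, 17 df |
|---|---|---|---|---|
| 140 men, plan's factor (140/1.4 = 100) | 1.40 | 3.333 | 85.6% (138 df) | 80.0% |
| 172 men, 8.6 per site | 1.76 | 3.295 | 84.8% | 79.0% |
| 140 men, 7 per site | 1.60 | 3.118 | 80.2% | 74.0% |

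The loss from the degrees of freedom is 5 to 6 points in every row. It is separate from the question of which cluster size belongs in the design effect, which accounts for the difference between the first and third rows.

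**Error rate if the mixed model is tested without a site-level correction.** A first approximation is the probability that a t variable on 17 df exceeds the uncorrected critical value. With the normal value 2.241 this is 3.9%; with patient-level t it is 3.7%. The fitted model behaves a little differently because the between-site variance cannot go below zero, so the planned model was also simulated (400,000 trials per setting, 20 sites averaging 7 or 8.6 men, correlation 0.1):

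| Estimator and reference | Error per nominal 2.5% test |
|---|---|
| REML, patient-level df or normal | 3.4-3.7% |
| Maximum likelihood, patient-level df or normal | 4.6-5.0% |
| REML, 17 df | about 2.3% |

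Over the two primary tests, the overall error could reach 2 × 3.4 = 6.8% to 2 × 3.7 = 7.4% under REML, or 2 × 4.6 = 9.2% to 2 × 5.0 = 10.0% under maximum likelihood, against the intended 5%. Maximum likelihood with 17 df still runs at about 3.3%, so the estimator needs naming as well as the df.

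**The two consequences are alternatives.** With 172 men and REML, simulated power is about 84% at an error rate of about 3.5% using patient-level df, and about 79% at about 2.3% using 17 df.

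**Minority analysis.** The plan does not show the inputs to its 78%. Section 12.7 implies 172 - 38 = 134 men who are non-White or Hispanic White. With DE 1.6, 134/1.6 = 83.75, which gives 78.2% on patient-level df and 71.9% on 17 df. With 134/20 = 6.7 per site, DE = 1.57 and power on 17 df is 72.8%.

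**The case against.** The best defence is that 12.2.1 does not prescribe a wrong test. A reader might infer from the sentence about the inferential unit that the final tests must use patient-level df. The documents do not support that. The sentence can simply mean that patients are the modelled observations, and the same section puts a random site intercept in the model, so between-site variation enters the standard error. Only the power calculation demonstrably uses patient-level df. This stands: the fault in 12.2.1 is silence, and the inflated error rates are conditional on how that silence is filled.

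The inflation also depends on the correlation. At 0.05 (an assumption) REML without correction gives about 2.9-3.2%, and at zero there is none. The 5.0% end needs maximum likelihood, which the plan does not mention.

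The power figures are conditional too. With 172 men and 17 df, power is 88% at a correlation of 0.05 and 70% at 0.15 (both assumptions). Twenty sites is an expectation and more may join: 24 sites (an assumption) would give 83.8% with 172 men. The shortfall is modest, and 12.2.2 reports that most earlier trials found gains of at least 10 points; at 10 points, power is 94% with 172 men on 17 df. All of this is fair. None of it rescues 85% power for the 8-point difference at a true 2.5% level under the assumptions the plan itself chose.

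**Conclusion.** The point holds. Under the plan's assumptions and equal sites, power on site-level df is about 79-80% rather than 85%, and 74% if only 140 men at 7 per site are scored. If the model is tested without a site-level correction, the higher apparent power is bought with tests running at about 3.4-3.7% (REML) or 4.6-5.0% (maximum likelihood). The plan cannot have 85% power and 2.5% tests together, but it does not suffer both losses together either.

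Two further readings should be resisted. A reader might infer that the race-specific analyses have only 5 site-level df, from the roughly 8 sites oriented to each of two groups. But 12.4.1 defines those subgroups by race, not by site type, and nothing excludes such men at other sites. A reader might also take a t-test on site means as equivalent to the mixed model. A two-sample version omits the other aid, and equivalence fails with unequal sites or the patient-level covariates that 12.2.1 permits.

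**What to change.** In 12.2.1, state that the model is fitted by REML and that each aid is tested, and its confidence interval formed, with Kenward-Roger, Satterthwaite or between-site df (about 17 with 20 sites, fewer if site-level covariates are added). Choose one before any outcome data are examined. Define the random intercept at the randomized unit, that is, the center together with any affiliates assigned with it. Apply the same rule to the linear mixed models in 12.4.2.

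In 12.2.2, restate power as about 79-80%, and 74% if only 140 men are evaluable, with the assumptions listed. In 12.4.2, recompute the 78% on the same basis and show the minority sample size and design effect used; it comes to about 72-73% on 134 men.

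The cost is a few sentences and one software option. The stated power becomes slightly less favourable. No extra patients are needed.
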